7 TREATMENT PLAN

All patients who qualify for this study will receive chemotherapy with ESHAP followed by treatment with Zevalin

7.A ESHAP REGIMEN DOSING

ESHAP chemotherapy: Patients will receive 2 cycles of cytoreductive chemotherapy according to the schedule described below. (Table 7)

TABLE 7 ESHAP CHEMOTHERAPY PLUS ZEVALIN

DRUG	DOSE	ROUTE	DAYS	INTERVAL
Etoposide	$40 \text{ mg/m}^{2/} \text{day}$	IV infusion over 1 hour	1,2,3,4	q 28 days for 2 cycles
Methylprednisolone	250 mg/day	IV push	1,2,3,4	q 28 days for 2 cycles
		_		
Cytarabine	2000 mg/m^2	IV infusion over 2 hours	4	q 28 days for 2 cycles
Cisplatin	25 mg/m ² /day	IV infusion at 1mg/min	1,2,3,4	q 28 days for 2 cycles

- The cycle length will be 28 days if bone marrow recovery allows. If recovery requires an additional week, then the second cycle will be postponed for a week.
- Either pegfilgastrim or filgastrim may be given at the investigator's discretion.

7.B RITUXIMAB, 111 IN ZEVALIN, AND 90 Y ZEVALIN ADMINISTRATION

The rituximab + ibritumomab tiuxetan regimen is given 4-6 weeks after completion of the second cycle of ESHAP. Treatment can be completed within 7 - 9 days in an outpatient setting

TABLE 8
Rituximab, 111In Zevalin, AND 90Y Zevalin Administration

AGENT	DOSE	ROUTE	DAYS	NOTES
Rituximab	250 mg/m ²	Slow IV	1, then 7, 8 or 9	Give prior to 111 In Zevalin
¹¹¹ In Zevalin	5 mCi	Slow IV push over 10 minutes	1	Give within 4 hours after rituximab
⁹⁰ Y Zevalin	Depends on platelet count (see Section 7.B.3)	Slow IV push over 10 minutes	7, 8, or 9	Give within 4 hours after rituximab

7.B.1 Rituxan & 111 In Zevalin Administration

1.6 mg of ¹¹¹In Zevalin (5.0 mCi of ¹¹¹In) will be used for radioimaging. The imaging dose of ¹¹¹In Zevalin will be administered by a 10-minute slow IV push injection immediately following the infusion of Rituxan. ¹¹¹In Zevalin may be directly injected by stopping the flow from the IV bag and injecting the radiolabeled antibody directly into the line. A 0.22 micron filter must be on line between the patient and the infusion port. Flush the line with at least 10 mL of normal saline after ¹¹¹In Zevalin has been injected. (See Appendix H).

a. Oral premedication (2 tablets [325 mg] of acetaminophen and 50 - 100 mg oral diphenhydramine hydrochloride) may be administered 30 - 60 minutes prior to starting each infusion of rituximab.

7.B.2 Radioimaging Schedule

Imaging (see Appendices H & I) will be conducted at the clinical site on each patient prior to receiving ⁹⁰Y Zevalin. Within 48-72 hours following the ¹¹¹In Zevalin administration, whole body anterior and posterior images of the patient must be acquired. If desired, a second image can be obtained at 90 - 120 hours to support the decision. If the patient has an altered biodistribution, the patient will be taken off study before proceeding to ⁹⁰Y Zevalin radioimmunotherapy.

a. Whole-body gamma camera images to assess biodistribution of ibritumomab tiuxetan are obtained as described below after the first infusion of rituximab followed by In-111 ibritumomab tiuxetan.

Scan 1	Hours 48 -72
Optional Scan	Hours 90 - 120

- b. If ibritumomab tiuxetan biodistribution is acceptable, therapy continues on Day 7, 8, or 9 with a second infusion of rituximab followed by Y-90 ibritumomab tiuxetan as noted in Table 8.
- c. **Altered biodistribution:** Y-90 ibritumomab tiuxetan should not be administered to patients with altered biodistribution of In-111 ibritumomab tiuxetan. The expected biodistribution of In-111 ibritumomab tiuxetan includes easily detectable uptake in the

blood pool areas on the first day image, with less activity in the blood pool areas on the second or third day image; moderately high to high uptake in normal liver and spleen during the first day and the second or third day image; and moderately low or very low uptake in normal kidneys, urinary bladder and normal bowel on the first day image and the second or third day image. Altered biodistribution of In-111 ibritumomab tiuxetan can be characterized by diffuse uptake in normal lung more intense than the liver on the posterior view of the second or third day image; or intense areas of uptake throughout the normal bowel comparable to uptake by the liver on the second or third day images.

7.B.3 Rituxan & 90Y Zevalin Administration

⁹⁰Y Zevalin will be administered following the second Rituxan infusion Day 7, 8 or 9 (See Appendix H). Each patient will receive one therapeutic dose of Zevalin according to the dosing schema (see Table 4 or Section 7.B.3b).

Please note: Patients with platelet counts from $100,000/\text{mm}^3$ to $149,000/\text{mm}^3$ will receive 0.3 mCi/kg and patients with platelet counts $\geq 150,000/\text{mm}^3$ will receive 0.4 mCi/kg, not to exceed 32 mCi $\frac{90\text{Y Zevalin}}{\text{Zevalin}}$. 90Y Zevalin will be administered intravenously as a slow IV push over 10 minutes. 90Y Zevalin may be directly infused by stopping the flow from the IV bag and injecting the radiolabeled antibody directly into the infusion port. A 0.22 micron filter must be on line between the syringe and the infusion port. Flush the line with at least 10 mLs of normal saline after 90Y Zevalin has been infused. (See Appendix H for radioincorporation methods)

There is no provision for additional treatment courses for patients entered into this protocol.

- a. Oral premedication (2 tablets [325 mg] of acetaminophen and 50 100 mg oral diphenhydramine hydrochloride) may be administered 30 60 minutes prior to starting each infusion of rituximab.
- b. Y-90 ibritumomab tiuxetan should be dosed at 0.4 mCi/kg (14.8 MBq/kg) actual body weight for patients with platelets counts ≥ 150,000/mm³ and at 0.3 mCi/kg (11.1 MBq/kg) actual body weight for patients with platelet counts of 100,000 149,000/mm³. The prescribed, measured and administered dose of Y-90 ibritumomab tiuxetan must not exceed the absolute maximum allowable dose of 32.0 mCi (1,184 MBq), regardless of the patient's body weight. Do not give Y-90 ibritumomab tiuxetan to patients with a platelet count < 100,000/mm³.
- c. Radiation Safety Precautions are minimal: No isolation required. Observe the following guidelines for 7 days after Y-90 Zevalin Patients should wash their hands thoroughly after urinationThe use of a condom is recommended during sexual intercourse to avoid transfer of body fluids. Avoid deep kissing. Throughout therapy and for up to 12 months following treatment, effective contraception is recommended.

d. Granulocyte colony stimulating factors may be given at the discretion of the treating physician to prevent or mitigate unacceptable granulocytopenia associated with fever, or granulocytopenia less than 500 granulocytes/µl. The use of G-CSF must be documented on the treatment summary form. Any toxicities associated with G-CSF must also be documented on the adverse event form.

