➤ Altered biodistribution

- Intense localization of radiotracer in the liver and spleen and bone marrow indicative of reticuloendothelial system uptake
- Increased uptake in normal organs (not involved by tumor) such as:
 - o Diffuse uptake in normal lung more intense than the liver.
 - o Kidneys with greater intensity than the liver on the posterior view.
 - o Fixed areas (unchanged with time) of uptake in the normal bowel greater than uptake in the liver.
 - o In less than 0.5% of patients receiving ¹¹¹In Zevalin (Ibritumomab Tiuxetan Indium), prominent bone marrow uptake was observed, characterized by clear visualization of the long bones and ribs.

If a visual inspection of the gamma images reveals an altered biodistribution, the patient should not proceed to the ⁹⁰Y Zevalin (Ibritumomab Tiuxetan Ytrium-90) dose. The safety and efficacy of the administration of ⁹⁰Y Zevalin (Ibritumomab Tiuxetan Ytrium-90)in patients with prominent marrow uptake is not known. Possible causes of prominent bone marrow uptake, such as bone marrow involvement by lymphoma, increased marrow activity due to recent hematopoietic growth factor administration, and increased reticuloendothelial uptake in patients with HAMA and HACA, should be considered. Re-assessment of biodistribution after correction of underlying factors should be performed. ⁹⁰Y Zevalin (Ibritumomab Tiuxetan Ytrium-90) should not be administered to patients with persistently prominent marrow uptake on the repeat biodistribution scans.

5.C.3 Day 7, 8 or 9

a. Rituximab Infusion & ⁹⁰Y Zevalin (Ibritumomab Tiuxetan Ytrium-90) Infusion (Please refer to section 7.B for detailed treatment administration)

5.C.4 Day 35 (+/- 7 days)

a. Laboratory tests including:

Complete blood count (CBC) with differential and platelet count. To be done every week until any count abnormalities have passed nadir.

5.D Restaging

5.D.1 3 Months Post-90Y Zevalin (Ibritumomab Tiuxetan Ytrium-90) Infusion

The following tests/evaluations will be obtained 3 months (+/- 7 days) post ⁹⁰Y Zevalin Infusion:

- a. History & Physical examination, including vital signs (BP, temperature & pulse), height, weight, Body Surface Area (BSA) & performance status (Appendix B).
- b. Laboratory tests including:
 - Complete blood count (CBC) with differential and platelet count
 - Serum chemistries BUN, creatinine
 - LDH
- c. Disease Assessment:
 - Total of all measurable indicator lesions.
 - CT or PET scan of the chest, abdomen and pelvis

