- d. Toxicity Assessment: Adverse events are to be recorded on an ongoing basis and on appropriate source documents at the clinical site and in the patient's case report form.

5.E Follow-Up Evaluations

5.E.1 Short-Term Follow-Up Period

- a. The following tests/evaluations will be obtained at 6-month intervals (+/- 7 days) for a period of 2 years (24 months) following the Zevalin:
 - History & Physical examination, including vital signs (BP, temperature & pulse), height, weight, Body Surface Area (BSA), and performance status (Appendix B).
 - Laboratory tests including:
 - o Complete blood count (CBC) with differential and platelet count
 - o Serum chemistries BUN, creatinine
 - o LDH
 - Disease Assessment (Only required at 6-month intervals for a period of 2 years (24 months) following Zevalin):
 - o Total of all measurable indicator lesions.
 - CT or PET scan of the chest, abdomen and pelvis (Restaging of disease by CT scan is recommended every 6 months up to Month 24, then annually until year 5).

5.E.2 Long-Term Follow-Up Period

- a. The following tests/evaluations will be obtained annually (+/- 30 days) for an additional 3 years after the completion of the Short-Term Follow-Up period:
 - History & Physical examination, including vital signs (BP, temperature & pulse), height, weight, Body Surface Area (BSA), and performance status (Appendix B).
 - Laboratory tests including:
 - o Complete blood count (CBC) with differential and platelet count
 - o Serum chemistries BUN, creatinine
 - LDH
 - Disease Assessment:
 - o Total of all measurable indicator lesions.
 - o CT or PET scan of the chest, abdomen and pelvis

Once the patients have completed the Short-Term Follow-Up period they will continue to be followed for 3 years on an annual basis (+/- 30 days) for survival and disease status. Patients should be followed by physical exam and, if clinically indicated by Good Medical Practice, CT or PET scans. Patients will be followed for 3 years or until patient starts alternate treatment or is removed from study to allow determination of study endpoints.

5.F Disease Progression Evaluations/Off-Study

Patients who develop disease progression during the treatment period and who do not begin other anti-cancer therapy will continue to be followed for routine safety and efficacy for a total of 30 days following any discontinuation of treatment for any cause.

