5.F.1 Tests to be Performed When a Patient is Determined to Have Disease Progression or is Removed from the Study for any Reason

The following tests will be performed within 4 weeks after a patient has demonstrated progression of disease, or removed from study:

It is strictly mandated that patients not be given other myelosuppressive anti-neoplastic agents until recovery from hematologic nadir.

These tests do not have to be repeated if they were performed within 7 days prior to documentation of disease progression.

- a. History & Physical examination, including vital signs (BP, temperature & pulse), height, weight, Body Surface Area (BSA), and performance status (Appendix B).
- b. Laboratory tests including:
 - Complete blood count (CBC) with differential and platelet count
 - Serum chemistries BUN, creatinine

• LDH

c.Disease Assessment (if patient is removed from the study for a cause other than progressive disease):

- Total of all measurable indicator lesions.
- CT or PET scan of the chest, abdomen and pelvis

d.Toxicity Assessment: Adverse Events (AE) are to be recorded on an ongoing basis until resolved or determined to be permanent. All AEs are to be documented on appropriate source documents at the clinical site and in the patient's case report form.

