The radiolabeling kits should be stored in a secure refrigerator at 2 - 8°C. Zevalin solutions are stable at 2 - 8°C for up to 8 hours for ⁹⁰Y Zevalin and up to 12 hours for ¹¹¹In Zevalin following their preparation. Due to the relatively short half life of the ⁹⁰Y isotope, if not used soon after calibration time, the actual dose will have decayed and will require recalculation. For proper Rituxan storage instructions see the package insert in the appropriate Appendix.

6.C.5 111In Zevalin and 90Y Zevalin Treatment Protocol

The ¹¹¹In and ⁹⁰Y isotope order form must be completed and faxed to the designated isotope vendor preceding the initial Rituxan infusion. Patients will receive an initial infusion of 250 mg/m² Rituxan. (111 In Zevalin, 90-Y-Zevalin, and Rituximab will not be provided by Biogen Idec

Incorporated). Immediately following, patients will receive a fixed dose of 5.0 mCi of ¹¹¹In Zevalin. If the biodistribution is altered such that the safety risk would be unacceptable, the patient will be taken off study and not proceed with ⁹⁰Y Zevalin radioimmunotherapy. On Day 7, 8 or 9, patients must receive a second infusion of 250 mg/m² of Rituxan and either 0.4 mCi/kg or 0.3 mCi/kg of Zevalin based on most recent platelet counts. The exact dose of Zevalin will be based on the patient's weight during the most recent evaluation according to Table 4. **The maximum dose is not to exceed 32 mCi of ⁹⁰Y.**

Table 4. Dosing of Zevalin

Platelet Counts ≥ 150,000/mm ³	Platelet Counts 100,000/mm ³ to 149,000/mm ³
0.4 mCi ⁹⁰ Y/kg	0.3 mCi ⁹⁰ Y/kg
Dose will be calculated using actual body weight	Dose will be calculated using actual body weight
Not to exceed 32 mCi (Maximum Dose)	Not to exceed 32 mCi (Maximum Dose)

6.C.6 Zevalin Adverse Events

For an extensive review of adverse events refer to the Investigational Brochure. Safety data, except where indicated, are based upon 349 patients treated in 5 clinical studies with ZEVALIN. In all cases, the ZEVALIN regimen included two doses of RITUXAN. See the RITUXAN package insert for specific adverse event (AE) information for that product.

Table 5 lists most common nonhematologic adverse events in \geq 5% of patients. The table does not include hematologic AEs of neutropenia, thrombocytopenia, and anemia (See Table 6, Hematologic Toxicity).

 $Table \ 5$ Incidence of Nonhematologic† Adverse Events in ≥ 5 % of Patients in Clinical Trials with ZEVALIN Regimen During the Treatment Period*(N = 349)

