11 REMOVAL OF PATIENTS FROM THIS STUDY

11.A Criteria for Discontinuation of a Patient's Study Participation

The date of discontinuation and reason(s) for patient discontinuation from the study will be recorded in the CRF. All evaluations which are required at the final study visit must by conducted for each patient who discontinues treatment, regardless of the reason (see Section 5.F.1).

- Disease Progression: Patients will be taken off study if they have progressive disease (PD) or clinically significant deterioration at any time during the study.
- Personal Reasons: Patients may choose to withdraw from the study at any time.
- Clinical Judgment of the Investigator: A patient may be withdrawn from the study, if in the opinion of the investigator, it is not in the patient's best interest to continue.
- Requiring other anti-neoplastic therapies

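### A patient who never receives 90Y Zevalin has no scheduled progression assessment beyond one off-study evaluation, yet enters a binomial 1-year PFS test with no rule for unknown status

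*Combined protocol and SAP*

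**What the plan says.** **Leaving without progression.** Section 7.B.2: "If the patient has an altered biodistribution, the patient will be taken off study before proceeding to" 90Y Zevalin. Section 6.C.5, where the altered biodistribution makes the risk unacceptable: "the patient will be taken off study and not proceed with" 90Y Zevalin. Section 5.C.2 is softer: it bars the 90Y dose but adds "Re-assessment of biodistribution after correction of underlying factors should be performed". Section 11.A adds "A patient may be withdrawn from the study, if in the opinion of the investigator" continuing is not in the patient's interest, and "Requiring other anti-neoplastic therapies".

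**What follows.** Section 5.F.1: "The following tests will be performed within 4 weeks after a patient has demonstrated progression of disease, or removed from study". This includes a disease assessment when the reason is not progression. The scheduled assessments run from Zevalin: 5.D.1 has "The following tests/evaluations will be obtained 3 months (+/- 7 days) post" 90Y Zevalin, and 5.E.1 has visits "obtained at 6-month intervals (+/- 7 days) for a period of 2 years (24 months) following the Zevalin". Section 5.E.2 ends long-term follow-up at alternate treatment or removal from study.

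**Others who do not receive 90Y Zevalin.** Section 3.A takes patients with more than 25% marrow involvement off treatment and follows them for progression and survival, without dates. Sections 4.A.12 and 7.B.3 set platelet, creatinine and bilirubin conditions for Zevalin but do not say what becomes of patients who fail them.

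**The analysis.** Sections 4.C and 12.B include every patient given one ESHAP dose and replace only those never treated. Section 12.C tests 1-year PFS as one binomial proportion at one-sided 0.10; Kaplan-Meier is named for the time-to-progression curve only. Appendix D, Table 2, counts PFS in all patients from trial entry. Section 3.B promises 5 years of follow-up after treatment so that endpoints can be determined.

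**The concern.** A binomial test needs a yes or no at 12 months for each of the 52 patients. A patient removed for altered biodistribution leaves at roughly the time 90Y would have been given, with one further assessment due within 4 weeks. Followed as written, the protocol stops collecting the primary endpoint months before it is determined, in a patient who must still be counted. That does not fit 3.B, 4.C, 12.B or Appendix D.

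Section 12.C does not say whether such a patient is a success, a failure or censored, nor how new therapy before progression is treated. Without a rule, the choice is made after the data are seen, and near the cut-off one patient can decide the trial.

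**Working it through.** **1. The plan's own figure.** Inputs from 12.B and 12.C: p0 = 0.50, p1 = 0.673, one-sided alpha 0.10, power 0.90.

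n = [(1.2816·√(0.5·0.5) + 1.2816·√(0.673·0.327)) / 0.173]² = 51.54, rounded up to 52. The sample size reproduces, with a known 12-month status assumed for everyone.

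Cut-off: 26 + 1.2816·√13 = 30.62, so at least 31 of 52. Exact type I error P(Bin(52, 0.5) ≥ 31) = 0.106; power P(Bin(52, 0.673) ≥ 31) = 0.906.

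**2. When contact is lost.** Take ESHAP completion as cycle 2 day 4 (day 32) or day 28 (day 56). Add 4 to 6 weeks (7.B) and regimen Day 7 to 9:

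- earliest: 32 + 28 + 6 = day 66
- latest: 56 + 42 + 8 = day 106

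That is about months 2.1 to 3.5 from cycle 1 day 1. The 5.F.1 window adds up to 4 weeks (0.9 month), so the last required assessment falls by about month 4.4, more than 7 months short of 12.

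**3. How many patients.** The only stated frequency is in 5.C.2: under 0.5%, for prominent marrow uptake. 52 × 0.005 = 0.26 expected; P(at least one) = 1 − 0.995^52 = 0.23. No rate is given for the other uptake patterns, for the platelet, creatinine, bilirubin or marrow conditions, or for the 11.A reasons.

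**4. Effect of k unknowns on the binomial rule.** k is assumed; the remaining 52 − k patients have rate p0 or p1.

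- As progression-free, type I error = P(Bin(52 − k, 0.5) ≥ 31 − k)
- As failures, power = P(Bin(52 − k, 0.673) ≥ 31)

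| k | Type I error, unknown = progression-free | Power, unknown = failure | Type I error, unknown = failure |
|---|---|---|---|
| 1 | 0.131 | 0.872 | 0.080 |
| 2 | 0.161 | 0.829 | 0.059 |
| 3 | 0.196 | 0.777 | 0.043 |

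Dropping the unknowns would contradict 4.C and 12.B.

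**5. Would Kaplan-Meier solve it?** Rule: the log-log one-sided 90% lower bound at 12 months must exceed 0.50. With complete data this gives the same cut-off (bound 0.503 at 31/52, 0.484 at 30/52). Simulation: exponential times, overall 1-year PFS held at p, k patients censored progression-free at 3.5 months, 20,000 runs.

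| k | Type I error, leaving unrelated to outcome | Power, leaving unrelated | Type I error, leavers' 1-year PFS 25% (assumed) |
|---|---|---|---|
| 1 | 0.076 | 0.863 | 0.092 |
| 2 | 0.090 | 0.882 | 0.127 |
| 3 | 0.103 | 0.889 | 0.167 |

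The two tables use different conventions. Here the overall rate is held at p, so under the null the remaining patients have a rate slightly below 0.50 (0.493 at k = 3). Giving the remainder rate p instead, type I error under unrelated leaving is about 0.08, 0.10 and 0.12. Kaplan-Meier therefore loses some power too, and it does not protect the error rate if leavers do worse.

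**The case against.** The strongest reply is that follow-up is not absent and the numbers are tiny. Section 5.F.1 gives a dated assessment, 3.A requires the marrow group to be followed, 3.B promises 5 years, and 13.C asks for forms at progression or death. A reader might infer that these patients have no progression follow-up at all; the documents do not support that. What they lack is a scheduled assessment after the off-study one. Neither 3.B nor 13.C supplies visit dates, and neither overrides an instruction to remove a patient from study.

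The point about numbers largely stands. On the stated rate, altered biodistribution affects 0 or 1 patient. In 1.D.2.c, all patients with dosimetry (205) met the criteria to proceed, although those were dosimetric limits, not the visual criteria used here. Two or three unknowns would need the routes that have no stated rate.

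Two other inferences fail. Section 3.A does not contradict 7.B.2, since it concerns a different group. Nor can patients below the platelet limit be said either to stay on study or to leave it; their disposition is not stated.

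Finally, 12.C presents the chi-square test as design characteristics, and Kaplan-Meier is already planned. But it is planned for time to progression and is not linked to the decision, so the gap remains.

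**Conclusion.** The concern holds in a limited form. Following the written rules loses 1-year status for some patients who must be counted, and the test has no rule for them. The sample size of 52 is not wrong on its own inputs.

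The likely effect is small and cannot be derived from the documents. The figures for 1 to 3 unknowns are illustrations resting on an assumed count; the Kaplan-Meier figures also rest on exponential times, censoring at 3.5 months and, in the last column, an assumed 25% rate in leavers. A reader might conclude that moving the decision to Kaplan-Meier settles the matter. It does not: with one unknown its power (0.863) is no better than counting a failure (0.872), and with three unknowns its type I error reaches about 0.17 if leavers do worse. Continued follow-up is the main remedy, and it is cheap enough to justify an amendment.

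**What to change.** 1. **Follow-up.** Reconcile 6.C.5, 7.B.2, 11.A and the follow-up stop in 5.E.2 with 3.B, 4.C and 12.B. Use off protocol treatment in place of off study, except where consent is withdrawn, and follow every ESHAP-treated patient for progression and death through the first assessment at or after 12 months. State the disposition of patients barred by platelets, creatinine or bilirubin, and reconcile the re-assessment wording in 5.C.2 with removal in 6.C.5 and 7.B.2. No treatment rule need change.

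2. **Visit dates.** For patients who do not receive 90Y Zevalin, time visits from trial entry or cycle 1 day 1. The date 90Y would have been given is undefined for someone who leaves during ESHAP. Keep intervals close to those of treated patients, but first reconcile 5.E.1 (scans every 6 months) with Appendix A, whose table as it reads marks scans at 3, 6 and 18 months after Zevalin and none at 12. The first treated-patient scan after month 12 is at about months 14.1 to 15.5 from cycle 1 day 1 under 5.E.1, but about 20.1 to 21.5 under the calendar.

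3. **Analysis rule.** In 12.C, fix before analysis how remaining unknowns and new therapy before progression are handled: for example, unknowns as failures in the binomial test with Kaplan-Meier at 12 months as sensitivity analysis, or the reverse.

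**Cost.** Amendment wording, a few extra routine scans and status checks, and some loss of power under either rule if unknowns remain: to 0.872, 0.829 or 0.777 as failures, or about 0.86 to 0.89 with Kaplan-Meier if leaving is unrelated to outcome.

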The above mentioned tests and assessment are to be performed within 28 days of Rituximab & Zevalin administration.

d. Rituxaimab Infusion (250 mg/m²) & ¹¹¹In Zevalin (Ibritumomab Tiuxetan Indium) infusion. (Please refer to section 7.B for detailed treatment administration)

5.C.2 Days 2, 3, 4 and 5

a. Gamma Scan: A scan is to be performed at 48-72 hours after ¹¹¹In Zevalin (Ibritumomab Tiuxetan Indium) infusion. Another optional scan may be performed at 90-120 hours after ¹¹¹In Zevalin (Ibritumomab Tiuxetan Indium) infusion.

CAUTION WILL BE TAKEN IN THE HANDLING OF ALL RADIOACTIVE SAMPLES ACCORDING TO STANDARD PROCEDURES AND PRACTICES AT THE CLINICAL SITE

The purpose of ¹¹¹In Zevalin (Ibritumomab Tiuxetan Indium) imaging is twofold:

- To evaluate biodistribution of whole body gamma camera images
- To assess whether biodistribution is acceptable to proceed with ⁹⁰Y Zevalin (Ibritumomab Tiuxetan Ytrium-90) radioimmunotherapy.

The biodistribution of ¹¹¹In Zevalin (Ibritumomab Tiuxetan Indium) should be assessed by a visual evaluation of whole body planar view anterior and posterior gamma images. A set of images at 48-72 hours after injection is required. To resolve ambiguities, optional images at other time points may be necessary. Images should be acquired using a large field of view gamma camera quipped with a medium energy collimator. Whole body anterior/posterior planar images should be acquired using a large field-of-view gamma camera and medium energy collimators. Suggested gamma camera settings: 256 x 1024 matrix; dual energy photopeaks set at 172 and 247 keV; 15% symmetric window; scan speed of 10 cm/min for the 48-72 hour scan, and 7-10 cm/min for subsequent scans.

> Expected biodistribution:

- Activity in the blood pool areas (heart, abdomen, neck, and extremities) may be faintly visible.
- Moderately high to high uptake in normal liver and spleen.
- Moderately low or very low uptake in normal kidneys, urinary bladder, and normal (uninvolved) bowel.
- Non-fixed areas within the bowel lumen that change position with time; delayed imaging as described above may be necessary to confirm gastrointestinal clearance.

Tumor uptake may be visualized in soft tissue as areas of increased intensity, and tumor-bearing areas in normal organs may be seen as areas of increased or decreased intensity. Tumor visualization on the ¹¹¹In Zevalin (Ibritumomab Tiuxetan Indium) scan is not required for ⁹⁰Y Zevalin (Ibritumomab Tiuxetan Ytrium-90) therapy.

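### Sections 5.C.2, 6.C.5 and 7.B.2 handle altered 111In biodistribution differently, and patients taken off study at this gate may lack the 1-year status that the primary analysis needs

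*Combined protocol and SAP*

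**What the plan says.** All references are to current text in the combined protocol and SAP.

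- **Bowel, 5.C.2.** The example of altered uptake is "Fixed areas (unchanged with time) of uptake in the normal bowel greater than uptake in the liver". The expected pattern includes "Non-fixed areas within the bowel lumen that change position with time" and also "Moderately low or very low uptake in normal kidneys, urinary bladder, and normal (uninvolved) bowel". The altered list for normal organs is introduced by "Increased uptake in normal organs (not involved by tumor) such as".
- **Bowel, 7.B.2 item c.** The example is "intense areas of uptake throughout the normal bowel comparable to uptake by the liver on the second or third day images", with no condition that the activity be fixed. This list is also illustrative: altered biodistribution "can be characterized by diffuse uptake in normal lung more intense than the liver", or by the bowel pattern.
- **Marrow.** 5.C.2 includes among the altered patterns that in under 0.5% of 111In recipients "prominent bone marrow uptake was observed, characterized by clear visualization of the long bones and ribs". It then says: "Re-assessment of biodistribution after correction of underlying factors should be performed", and withholds 90Y if the uptake persists on the repeat scan. 7.B.2 does not name marrow and describes no re-assessment.
- **Consequence.** 5.C.2 says the patient should not go on to 90Y. 7.B.2 takes any patient with altered biodistribution off study. 6.C.5 does so when the alteration makes the safety risk unacceptable.
- **Analysis set and follow-up.** Sections 4.C and 12.B keep everyone with at least one ESHAP dose in the analysis. After removal from study, 5.F.1 requires one set of tests within 4 weeks, including disease assessment if the reason was not progression. Section 3.A treats the comparable marrow-involvement gate differently: those patients stop treatment but are still followed for progression and survival.

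**The concern.** This is the imaging gate before the radioactive therapeutic dose. No section is said to prevail, so two readers holding the same borderline scan could choose differently between giving 90Y, imaging again and removing the patient.

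The larger statistical issue is the off-study consequence. A patient stopped at the gate has already had ESHAP and so counts in the primary 1-year PFS analysis. Removal from study takes that patient out of scheduled follow-up well before 12 months. Section 12.C describes a one-sample binomial chi-square test and gives no rule for a patient whose 1-year status is unknown.

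**Working it through.** **1. The plan's own figure.** With p0 = 0.50, p1 = 0.673, one-sided alpha 0.10 and power 0.90 (12.B, 12.C):

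n = [(1.2816 × √(0.50 × 0.50) + 1.2816 × √(0.673 × 0.327)) / 0.173]² = 51.5, rounded up to 52. Power at n = 52 is 0.902. The planned 52 reproduces, and nothing below changes it.

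**2. The sections side by side.**

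| | 5.C.2 | 7.B.2 | 6.C.5 |
|---|---|---|---|
| Bowel example | Fixed and above liver | Intense, throughout the bowel, at liver level | None |
| Non-fixed bowel activity | Expected | Not addressed | Not addressed |
| Prominent marrow uptake | Altered; correct the cause, re-assess, withhold if persistent | Not named | Not named |
| Consequence of an altered scan | No 90Y | No 90Y, off study | No 90Y, off study if risk unacceptable |

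Three cases show where the text leaves room:

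- Intense bowel uptake throughout, equal to liver but not above it, matches the 7.B.2.c example and not the 5.C.2 example.
- Prominent marrow uptake with a correctable cause is re-assessed under 5.C.2. Under 7.B.2 the patient leaves the study if the scan is classed as altered.
- An altered scan judged an acceptable risk leads off study under 7.B.2 but is not covered by the 6.C.5 sentence.

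The 5.C.2 condition that uptake be unchanged over time also needs two images, while only the 48–72 h image is required.

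**3. Expected marrow cases.** The input is the 5.C.2 rate, taken at its upper edge of 0.005.

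- All 52 imaged: 52 × 0.005 = 0.26 expected; P(at least one) = 1 − 0.995^52 = 22.9%.
- 40 imaged (an assumed number, since some patients will not reach the scan): 0.20 expected; P(at least one) = 18.2%.

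Because the quoted rate is below 0.5%, these are upper figures at that rate. The documents give no bowel rate, so no bowel count is possible.

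**4. Last required assessment after removal at the gate.** Count the first ESHAP dose as day 1, with no cycle delay. Completion of ESHAP is either day 32 (last dose of cycle 2) or day 56 (end of cycle 2). Add 28 to 42 days to 111In, 2 to 5 days to the scan, and up to 28 days for the 5.F.1 tests.

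| Completion of ESHAP | Earliest 111In and scan | Latest 111In and scan |
|---|---|---|
| Day 32 | 32 + 28 + 2 + 28 = 90 | 32 + 42 + 5 + 28 = 107 |
| Day 56 | 56 + 28 + 2 + 28 = 114 | 56 + 42 + 5 + 28 = 131 |

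At 30.4 days per month, day 90 is 3.0 months, day 107 is 3.5 and day 131 is 4.3. A one-week delay of cycle 2 adds 7 days, to at most day 138. The endpoint is at 12 months.

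No other section clearly fills the gap. The 5.E.1 visits are timed from Zevalin, the 3.B follow-up runs from completion of treatment, and 5.E.2 follow-up stops on removal from study.

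**5. Effect on the primary test.** Under the null the expected count is 26 and the variance is 52 × 0.25 = 13.

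- 31/52: z = (31 − 26)/√13 = 1.387, one-sided p = 0.083.
- 30/52: z = (30 − 26)/√13 = 1.109, one-sided p = 0.134.

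One patient of unknown status changes the conclusion only if the other 51 contain exactly 30 who are progression-free at 1 year.

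**The case against.** **Bowel.** Both sections expect moderately low or very low uptake in normal bowel, and both altered lists are examples. A reader might infer that liver-level bowel uptake is acceptable under 5.C.2. The text does not support that, because such uptake is outside the expected pattern there too. A reader who applies both sections would withhold 90Y, which is the safe direction. This largely stands; what remains is two different stated thresholds for one scan.

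**Marrow.** 7.B.2 never mentions marrow, so the conflict appears only when the sections are read together, and the specific 5.C.2 rule can be taken to govern. A reader might also infer that 7.B.3, which provides for no additional treatment courses, blocks a repeat scan. That sentence follows the rule of one therapeutic dose and concerns therapy, not imaging. Growth factor allowed with ESHAP (7.A) might suggest a higher marrow rate than quoted, since 5.C.2 names recent use as a possible cause. But 111In comes 4 to 6 weeks after ESHAP, and the documents give no rate for that setting.

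**Consequence.** A reader might infer that 6.C.5 lets an altered scan of acceptable risk proceed to 90Y. It does not say so, and 5.C.2 and 7.B.2 both withhold.

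**Follow-up.** Section 11.A removes patients for other reasons too, so the gap is wider than this gate. Section 3.B promises 5 years of follow-up to determine endpoints, and the stop on removal is written in the long-term section. These points soften the criticism but do not answer it: 3.B is tied to completing treatment, which a patient stopped at the gate has not done. Here the protocol itself mandates the removal, and 3.A already has the better rule for a comparable gate.

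**Conclusion.** The point holds in a limited form. The three sections differ on the example bowel threshold, on re-assessment of marrow uptake and on who goes off study. All withhold 90Y for a clearly altered scan, so the safety ambiguity covers only borderline bowel uptake and marrow uptake with a correctable cause. Fewer than 0.26 marrow cases are expected among 52 patients, assuming that the quoted rate below 0.5% applies here. The bowel number is unknown.

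The stronger part is follow-up. Followed as written, the off-study rule leaves a patient in the 1-year PFS analysis with a last required assessment about 3 to 4 months after the first ESHAP dose. The latest date is day 107 or day 131 according to the reading of completion of ESHAP, without delays.

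A reader might go further and infer that the primary test is undermined or the trial underpowered. The figures do not support that: sample size and power are unchanged, and a single unknown status matters only at the 31/52 boundary. It should be corrected because the correction is cheap and protects both the gate and the completeness of the primary endpoint.

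**What to change.** 1. In 6.C.5 and 7.B.2, replace removal from study with the 3.A rule: off treatment, but still followed for progression and survival, with disease assessments at the existing calendar intervals.
2. Keep one criteria list in 5.C.2 and have 6.C.5 and 7.B.2 item c refer to it. For bowel, withhold 90Y if either existing criterion is met, in the protocol's own words and keeping the 7.B.2.c condition that uptake is throughout the bowel. Allow an exception if the already permitted 90–120 h image shows non-fixed luminal activity. The nuclear medicine investigators should confirm this rule.
3. State that the 5.C.2 re-assessment rule governs prominent marrow uptake and that 90Y is withheld if the uptake persists.

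The cost is amendment wording in three sections. The bowel rule uses a scan that is already allowed, and the few patients stopped at the gate would have disease assessments at intervals already in the calendar.
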